13. ANALYSIS

The trial has sufficient resources to enroll 150-176 participants who will be randomly allocated to 1 of 2 sequences for each of the two groups: (1) the Self-Directed group or (2) the DASH intervention group.

Power and sample size

A. Aim 1 Immediate Effects: Clinical Outcomes (Effectiveness)

- 1. Primary endpoint: The proposed study is powered for office SBP. Based on the 12-week SBP means and variances from the DASH-Sodium trial,⁶ with 75 people in each arm, we will be able to detect a difference in SBP of -5.8 mm Hg (type 1 error of 0.05, power of 0.85). The 12-week between-group difference in SBP in DASH-Sodium was -8.9 mm Hg.
- 2. Secondary endpoints: We will have adequate power to detect small differences (i.e., <15%) in awake-time SBP, BMI, cholesterol, triglycerides, and hemoglobin A1c.
- B. Aim 2 Immediate Effects: Behaviors (Adoption)

We will be able to detect changes of 13.0% to 29.5% in self-reported fruit and vegetable intake, urine sodium and potassium, and home-prepared dinners per week. These differences are smaller in magnitude than actual differences observed in prior trials.^{29,30}

Analysis Plan (RE-AIM Framework)

Reach. As in prior work, we will quantify recruitment yields and engagement. 52,53

Effectiveness & Adoption. The analysis will be conducted by the Statistical Core under the intent-to-treat principle for both effectiveness and adoption endpoints. The residual distribution of all outcomes will be checked for normality and log-transformed where appropriate. For the Primary Aim, we will use generalized estimating equation (GEE) models with a treatment-by-visit interaction term. The visit term will be used to compare changes on office SBP between 3 months versus baseline, 6 months versus 3 months, and 6 months versus baseline with a product (interaction) term to compare changes across intervention assignment (DASH vs self-directed shopping). Models will be adjusted for ZIP code or baseline BP in sensitivity analyses. Continuous variables will be analyzed with a Gaussian distribution, identity link, while dichotomous variables will be analyzed with a binomial distribution, logit link.

Implementation. Quality-of-life and cost data will be used to analyze health economic data and budget impact, based on cost per HTN case prevented and 10-year cost per quality-adjusted life-year gained.

Maintenance. In qualitative analyses, a coding dictionary will be developed and implemented based on review of the transcripts' content and interview questions. Codes will denote content of questions, GTE and PRISM domains/principles, and concepts naturally emerging from discussion. During the coding process, inter-rater reliability will be established by comparing the agreement in coded text with 20% of the transcripts between coders. Coding differences will be

resolved through consensus via regular and iterative discussions. A qualitative database will be compiled, coded, and analyzed using qualitative software (NVivo). We will use text retrieval and grouping functions on specific codes and combinations of codes for a particular topic and summarize the issues, agreements, and disagreements in content for each item. This process will result in a list of themes related to intervention acceptability³¹ and determinants (barriers and facilitators) of DASH eating plan sustainability. As we summarize and interpret, we will identify findings or patterns among themes and will review data for statements that directly confirm or discredit our interpretations.⁵² This theme-focused analysis will provide qualitative data to be integrated with our quantitative findings and guide refinement of the intervention.

Missing data

Based on the existing literature, we will employ recommended strategies to address missing data. ^{63,64,65,66} However, every effort will be made to collect outcome data on all participants.

14. DATA MANAGEMENT

Data will be collected from the following main sources: 1) Data collected by trial staff on trial forms for later entry or directly inputted into the data management system (DMS)/REDCap; 2) Data from Quest laboratories electronically available for upload; 3) Data from Spacelabs ambulatory BP monitoring devices available for direct upload; 4) Data from the Automated Self-Administered 24-Hour (ASA24®) Dietary Assessment Tool, estimating the nutrient content of consumed foods, and 5) Data derived from ESHA software, estimating the nutrient content of the intervention; 6) Data collected from self-administered forms; and 7) Data collected via our online Qualtrics (Seattle, Wa) screening survey or a recruitment tracking Excel database. The DMS will be accessible only via the secure website and only to authorized personnel. Data entered into the DMS will be subject to intra- and inter-item checks, such as range checks, logic checks, and consistency checks. Missing data items will be noted in the database, although certain key values (e.g., BP measurement) will not be allowed to be marked 'missing.' Data entry staff will perform data entry as soon as possible after data has been collected (within one week).

Recruitment data for tracking enrollment sources and goals will be managed separately in a secured team folder. All laptops are password protected and encrypted.

Data confidentiality and integrity

The investigative team, including staff at all levels of the study, will be trained in the importance of data integrity and maintaining participant confidentiality, including HIPAA (Health Insurance Portability and Accountability Act). All data will be stored on secure servers. All study-related computers will be located behind appropriate firewalls and will maintain automated virus update mechanisms. Printed materials will be maintained in locked rooms and file cabinets accessible only to the study team. All staff will sign statements attesting to their understanding of and willingness to abide by policies regarding confidentiality and data integrity.

Trial-wide data release

De-identified trial data will be shared with external investigators on an individual basis through contact with the trials' principal investigator.

15. COLLABORATIONS

GoFresh and GoFreshRx

As a sister study to GoFresh, GoFreshRx has adopted standardized data elements that correspond with the GoFresh project to enable cross-study comparisons of the various

implementation strategies. GoFreshRx study team will compare de-identified, common data elements with GoFresh to facilitate pooled analyses and ancillary studies.

GoFreshRx focuses on adults with treated hypertension funded by the National Institute of Minority Health and Health Disparities, using a similar intervention and design, focused on Black adults with treated hypertension. Instruments for both trials will be shared to facilitate pooled analysis of data elements.

16. TIMELINE

The trial consists of four main phases: (1) Protocol development with IRB review (year 1, quarters 1-3); (2) Intervention development (year 1, quarters 2-4); (3) Recruitment, randomization, and follow-up (year 1, quarter 4 to year 5, quarter 2); and (4) Data analyses and dissemination (year 3, quarter 3 to year 5, quarter 4). Qualititative interviews occur in years 1-4 with analysis in year 5.

Table. Timeline	Year 1		Year 2			Year 3			Year 4				Year 5							
Calendar Year	1/1	/22-:	12/31	1/22	1/1	/23-1	L2/31	./23	1/1	/24-1	12/31	/24	1/1	/25-1	2/31	L/25	1/1	/26-:	12/31	/26
Quarters	1	2	3	4	1	2	3	4	1	2	3	4	1	2	3	4	1	2	3	4
Protocol Development																				
Intervention Development																				
Recruitment, Randomization, Follow-up																				
Qualitative Interviews																				
Data Analysis, Publication, and Dissemination																				

#### 1 Introduction

GoFreshRx is an individual level, randomized feeding trial to determine the effect of 12 weeks of dietitian-assisted DASH-patterned grocery shopping on seated blood pressure in 150-176 adults in the ages of 18-100 years who are actively taking a stable dose of blood pressure medications. Participants are randomly assigned to one of 2 groups: (1) Dietitian-assisted, DASH-patterned grocery shopping or (2) Self- directed grocery shopping group. The trial is organized into two phases: the intervention phase (assessed at 3 months) and the observation (maintenance) phase with physical assessments at 6-months and behavioral assessments at 6 and 12 months. The primary trial analysis described in this document focuses on physical assessments at 3 and 6 months. Other outcome assessments performed during the study (i.e., qualitative interviews as well as questions related to quality of life, grocery shopping and dining habits, and perceived stress) are not planned as part of this analysis.

The primary outcome is the net effect of DASH groceries with reduced sodium, DASH-patterned groceries versus self-directed grocery shopping on 12-week seated systolic blood pressure (as measured at 3 months, the end of the intervention phase).

#### 1.1 Primary aim

To determine the effects of 12-weeks of dietitian-assisted, home-delivered, virtually-ordered, low sodium, DASH groceries compared with self-directed grocery shopping (DASH education and a \$500/month stipend over 3 months) on seated office systolic blood pressure among Black adults with treated stage 1 or stage 2 hypertension.

In this randomized controlled trial (RCT) of at least 150 participants, we will compare the DASH grocery intervention versus the self-directed group over 12 weeks to determine its effect on seated systolic blood pressure.

#### 1.2 Other aims

To estimate the effects of the DASH grocery intervention on the following secondary outcomes:

- Measured at 6 months (observation phase):
  - Seated, office-based, systolic blood pressure (SBP)
- Measured at 3-month and 6-month visits (intervention & observation phase):
  - Seated, office-based, diastolic blood pressure
  - Ambulatory blood pressure monitoring (ABPM): wake-time systolic and diastolic blood pressure
  - Body Mass Index (BMI)
  - o 24-hour urine sodium
  - 24-hour urine potassium
  - Hemoglobin A1c

- Lipids: total cholesterol, high density lipoprotein cholesterol, derived low density lipoprotein cholesterol, and triglycerides
- Serum potassiumSerum creatinine
- Daily intake of fat, fruits, and vegetables
- 24-hour dietary recall

#### 2 Data Source

Data pertaining to the recruitment drive of the GoFreshRx Trial will be managed in a secure Excel document that will be accessible to team members for tracking recruitment activities. These data include the total number of inquiries (both enrolled and non-enrolled persons).

Data for all screened and randomized participants will be entered by clinic staff into a REDCap dataset (Vanderbilt University, Nashville, Tennessee). REDCap is a secure, password-protected, web-based, research data capture and management application, hosted by the REDCap eData Collection Core of Beth Israel Deaconess Medical Center.

Grocery nutrient information will be derived from the ESHA Research platform (Beaverton, Oregon) and Nutrition Data System for Research (NDSR, University of Minnesota, Minneapolis, Minnesota). Backup files of the database will be generated and stored at regular intervals in a secure, independent location, to permit regeneration of the database in the event that it is destroyed. Data from ambulatory blood pressure monitoring (ABPM) (Sentinel, Spacelabs Healthcare, Snoqualmie, Washington), laboratory results (Quest Diagnostics, Secaucus New Jersey), and the Automated Self-Administered 24-hour Dietary Assessment Tool (ASA24, U.S. Department of Health and Human Services, Washington D.C.) will be regularly uploaded into REDCap to create a centralized analytic dataset.

### 3 Primary Outcome: Seated Blood Pressure

#### 3.1 Randomization and primary analysis

Participants will be randomized using a permuted block scheme (sizes of 2, 4, or 6) through a randomization feature embedded in REDCap in strata of baseline BP (SBP 120 to <140 mm Hg or 140 to <150 mm Hg). Blood pressure will be used as a stratification variable to ensure that people with varying degrees of hypertension are evenly distributed between interventions.

Randomization assignments will follow a 1:1 ratio such that half of participants will be assigned to order home-delivered, low-sodium, DASH-patterned groceries with the assistance of a registered dietitian over a 12-week period. The other half will be assigned to self-directed grocery shopping. This group will receive a handout about the DASH diet and receive a \$500 monthly stipend for 3 months.

#### 3.2 Primary analysis

Our primary comparison is the net effect of randomized assignment (dietitian-assisted vs. self-directed shopping) on office SBP from baseline to 3- (primary) and 6-months post-randomization. Office SBP will be based on the average of three visits at baseline (two screening visits and the randomization visit each with 3 measurements; nine measurements total), two 3-month follow-up visits (each with 3 measurements; six measurements total), and two 6-month follow-up visits (each with 3 measurements; six measurements total). We will first confirm that the residuals of office SBP are normally distributed (if not it will be log-transformed). Modeling will be performed using generalized estimating equation (GEE) models with a treatment-by-visit interaction term. We will perform an intent-to-treat analysis. The visit term will be used to compare changes between 3 months versus baseline, 6 months versus 3 months, and 6 months versus baseline with a product (interaction) term to compare changes across intervention. Models will be adjusted for ZIP code or baseline blood pressure in sensitivity analyses.

Our hypothesis is that 12 weeks of dietitian-assisted, home-delivered, low sodium, DASH groceries will lower office SBP compared to 12-weeks of self-directed grocery shopping. The null hypothesis is that there will be no difference in office SBP between the two intervention arms. The comparison between the two treatment groups will be performed by comparing the regression coefficient for treatment with zero (a two-sided alpha of <0.05 will be considered statistically significant for the primary comparison at 3-months.

For additional pre-specified sensitivity analyses and subgroups to assess effect medication, see below.

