5. STUDY POPULATION AND ELIGIBILITY

Eligibility criteria are summarized below. This trial focuses on hypertension in the setting of active stable blood pressure medication use. We will include families with less than or equal to 6 adults at dinner time to allow for sharing (a child less than 18 is counted as half an adult), while maintaining adequate food for the study participant.

Inclusion criteria

- Age 18 to 100 years
- Self-reported/self-identified as Black or African American
- Active treatment with medications intended for hypertension treatment within the last 6 months at stable doses
- Resting SBP of 120 to <150 mm Hg and DBP <100 mm Hg based on the cumulative average across three pre-randomization visits
- Residence in communities identified by the Massachusetts Department of Public Health as Suffolk County (Boston area) food deserts: Brighton, Chelsea, Dorchester, East Boston, Everett, Hyde Park, Jamaica Plain, Malden, Mattapan, Revere, Roslindale, Roxbury, or Winthrop
- Able to receive home-delivered groceries or pick them up at a convenient location and willing to eat only the groceries provided over a 12-week period
- Have access to refrigeration, cooking appliances, and Wi-Fi/cellular service
- Have access to mobile device or computer to be able to conduct grocery orders via video conference or by phone
- Willing and able to complete required measurement procedures

Exclusion criteria

Laboratory Exclusions:

- Serum potassium ≥5.0 mmol/L or <3.5 mmol/L
- Estimated glomerular filtration rate (eGFR) <30 mL/min per 1.73 m² by the Chronic Kidney Disease Epidemiology Collaboration (CKD-EPI) 2021, race-free, creatinine-based equation
- Hemoglobin A1c ≥6.5%

Medication Exclusions:

 Unstable doses of medications that lower BP or medications intended for hypertension treatment (including antihypertensives taken for non-hypertension purposes) within the last 6 months

- Unstable doses (i.e., a change in the 2 months prior to screening or randomization) of the following:
 - Sodium-glucose co-transporter 2 (SGLT2) inhibitors
 - Stimulants
 - Inhaled or oral medications for asthma or chronic obstructive pulmonary disease (COPD)
 - Hormone replacement therapy or thyroid hormone
 - Weight-increasing psychotropic agents, including antipsychotic agents, lithium, and mirtazapine
- Use of any of the following medications:
 - Potassium supplement, except if part of a multivitamin
 - Warfarin (Coumadin)

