#### 3.3 Power and sample size

The primary outcome is change in SBP between the two randomized assignments. Our power calculation is based on the 12-week means and variances from the DASH-Sodium trial, where the 12-week between-group difference in SBP was -8.9 mm Hg. With 75 people in each arm, we will have sufficient power to detect a difference in SBP of -5.8 mm Hg (type 1 error of 0.05, power of 0.85; assuming a standard deviation of 11.85 and 11.4 for control and intervention groups based on the DASH-Sodium trial). We will over-recruit up to at least 176 participants to account for a 15% attrition rate.

With respect to secondary endpoints, we will have sufficient power to detect small differences of 15% or less in the following secondary endpoints: wake-time SBP, BMI, cholesterol, triglycerides, and hemoglobin A1c. Regarding adherence, we will be able to detect changes of 13.0%–29.5% in self-reported fruit and vegetable intake, urine sodium and potassium, and 24-hour recall potassium. These differences are smaller in magnitude than the actual differences observed in prior trials.

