#### 4.2 Secondary Endpoints

We will examine the effect of the DASH-patterned grocery intervention on the following additional outcomes, testing the null hypothesis that there is no difference in the following outcomes between the DASH-patterned groceries and the self-directed intervention. We will examine the distribution of all variables. We will use generalized estimating equations with a robust variance estimator and a normal family identity link for normally distributed outcomes or a binomial distribution, logit link for binary outcomes. A visit term will be used to compare changes between 3 months versus baseline, 6 months versus 3 months, and 6 months versus baseline with a product (interaction) term to compare changes across intervention. Continuous variables with non-normal residuals will be log-transformed with effects reported as a percent change. If residuals are still not normally distributed even after log transformation, we will apply non-parametric approaches.

- Seated, office-based, diastolic blood pressure: This will be based on the average of three visits at baseline (two screening visits and the randomization visit each with 3 measurements; nine measurements total), two 3-month follow-up visits (each with 3 measurements; six measurements total), and two 6-month follow-up visits (each with 3 measurements; six measurements total). This is a continuous variable that we anticipate will follow a normal distribution.
- Ambulatory blood pressure monitoring: We will determine the mean waketime systolic and diastolic blood pressure (intervention & observation phases) measured at baseline, 3-months, and 6-months after randomization. This is a

continuous variable that we anticipate will follow a normal distribution.

- Body Mass Index (BMI): This is derived from a height measurement at baseline and two weight measurements at baseline, 3-months, and 6-months. This is a continuous variable that we anticipate will follow a normal distribution.
- 24-hour urine potassium/creatinine and sodium/creatinine ratio: This is collected after a clinic void over a 24-hour period at baseline, 3-months, and 6-months. These continuous variables are often skewed and may require log-transformation in which case they will be reported as a percent change. We will examine potassium/24hr period and sodium/24hr period as well.

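### A normality check with no stated criterion decides whether the primary SBP result is a mm Hg difference or a ratio of geometric means

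*SAP*

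**What the plan says.** SAP 3.2 makes the scale of the primary outcome conditional: "We will first confirm that the residuals of office SBP are normally distributed (if not it will be log-transformed"). Protocol section 13 (Analysis Plan, Effectiveness & Adoption) has the general form, "The residual distribution of all outcomes will be checked for normality and log-transformed where appropriate", and a few sentences later says "Continuous variables will be analyzed with a Gaussian distribution, identity link". Neither document gives a test, plot or cut-off. Neither says whether the residuals come from all visits or from 3 months only, or whether the person judging them is blind to arm.

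The design is written in mm Hg. SAP 3.3 says "The primary outcome is change in SBP between the two randomized assignments" and "we will have sufficient power to detect a difference in SBP of -5.8 mm Hg", "assuming a standard deviation of 11.85 and 11.4 for control and intervention groups based on the DASH-Sodium trial", and sets this against a DASH-Sodium difference of -8.9 mm Hg. SAP 4.2 provides for a robust variance estimator, and for percent-change reporting after a log transform, but only for the secondary endpoints. SAP 3.2 has neither. It does not say how a logged primary result would be reported, or that the mm Hg result would still be given.

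Eligibility limits baseline: "Resting SBP of 120 to <150 mm Hg and DBP <100 mm Hg", averaged over the pre-randomization visits. Follow-up SBP has no such limit, and the SAP 3.2 model treats baseline as one of the visits.

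**The concern.** The two branches of the rule estimate different quantities. On the natural scale the result is a between-arm difference in mean change, in mm Hg. On the log scale it is a ratio of geometric means. Only the first can be set directly against -5.8 and -8.9 mm Hg. With no criterion, two competent analysts could follow the text on the same data and report different primary estimands.

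The check also protects against little. At about 75 per arm, inference on a mean difference from GEE with an identity link and a sandwich variance rests on large-sample behaviour and does not require normal residuals. Pooling baseline values confined to 120 to <150 mm Hg with unrestricted follow-up values can fail a normality test without any defect in the mm Hg comparison.

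**Working it through.** **1. The plan's own figure.** Inputs from SAP 3.2 and 3.3: 75 per arm, difference 5.8, SDs 11.85 and 11.4, two-sided alpha 0.05, power 0.85.

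- Root-mean-square SD = √[(11.85² + 11.4²)/2] = 11.63.
- SE = 11.63 × √(2/75) = 1.899. Power = Φ(5.8/1.899 − 1.960) = 0.863 (0.859 with the noncentral t).
- With a common SD of 11.85, SE = 1.935, power = 0.850 and the detectable difference is (1.960 + 1.036) × 1.935 = 5.80.
- Attrition: 150/0.85 = 176.5, against the stated 176.

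The mm Hg design reproduces.

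**2. What the target becomes after a switch.**

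- 5.8/120 = 4.8%; 5.8/135 = 4.3%; 5.8/150 = 3.9%.
- Conversely, one ratio of 1 − 5.8/135 = 0.957 means −5.2 mm Hg at a mean of 120 and −6.4 mm Hg at 150.
- Log-scale power at a control mean of 135, by the delta method: effect −ln(1 − 5.8/135) = 0.0439; SDs 11.85/135 and 11.4/129.2, root-mean-square 0.0880; power 0.863.

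Power is unchanged; the quantity and its units are not.

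**3. How often the switch might occur.** The documents give no test, so these figures are illustrative. Assumptions: Shapiro-Wilk at 0.05, 75 per arm, residuals about arm-by-visit means.

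With normal SBP, baseline truncated to 120 to <150 (SD about 7.7), follow-up SD 9-12 and 2,000 trials in each of three variance settings, pooled residuals failed in 15.5%, 14.1% and 33.9% of trials. The two scales disagreed on 3-month significance in 0-0.6%.

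A second set used baseline and 3-month visits, baseline mean about 132 before truncation, 3-month SD 11.6, correlation 0.5 and 5,000 trials per case. The rule was applied to pooled residuals:

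| 3-month error | Switch, pooled | Switch, 3-month only | Type I error of rule | Power, mm Hg / rule | Scales disagree (null / −5.8) |
|---|---|---|---|---|---|
| Normal | 24% | 4% | 0.047 | 0.937 / 0.937 | 0.7% / 1.0% |
| Right skew 0.7 | 74-75% | 54-55% | 0.052 | 0.938 / 0.949 | 0.7% / 1.4% |
| Right skew 1.0 | 90% | 80% | 0.051 | 0.934 / 0.947 | 0.8% / 1.6% |

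Simulated power exceeds 0.85 because, under the assumed correlation, change varies less than the SDs in the plan.

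**The case against.** The rule, its order and its direction are written in advance; it is not a choice made by looking at the effect or the p-value. A statistician reading a Q-Q plot might seldom trigger it, so the percentages above describe an assumed test, not this plan. The stated null of no difference in office SBP is not tied to a scale. The 10 mm Hg medication adjustment, and the linear adjustment given beside it, act on the measurement and could be made before logging. All of this stands. It limits the point but does not supply the missing criterion or guarantee a mm Hg estimate.

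Several stronger readings are tempting and are not supported:

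- A reader might infer that the eligibility range makes non-normal residuals inevitable. It does not. Under normal SBP most simulated trials pass even when visits are pooled, and with 3-month residuals alone the failure rate is close to the nominal test level.
- A reader might infer that logging makes the residuals worse. That depends on the unknown shape. With three visits pooled (same assumed SD and correlation, 1,500 trials), failure after logging rose from 16% to 52% for normal errors, but fell from 56% to 17% with right skew of 0.4 and from 90% to 39% with skew of 0.7.
- A reader might extend the criticism to the secondary endpoints, where SAP 4.2 says "If residuals are still not normally distributed even after log transformation, we will apply non-parametric approaches". That section already gives an expected scale for most outcomes and a reporting rule after logging, and a rank test on change scores does compare change between arms.

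**Conclusion.** The point holds as one about the estimand and its units. SAP 3.2 and Protocol section 13 leave the scale of the primary result to an undefined check made after the data are seen, and nothing guarantees the mm Hg difference on which the trial was sized.

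Under the assumed test and normal SBP, the switch would occur in roughly 15-35% of trials with pooled visits and about 5% with 3-month residuals only, and more often under right skew. These rates depend on the assumed test, variances, correlation and error shape.

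It should not be read as an error in power, sample size or type I error. The stated power reproduces, type I error of the rule stayed at 0.047-0.052 in the tabulated cases, power moved by at most about 1.5 points, and the scales disagreed on significance in about 1-2% of trials or fewer. The change is still worth making, because it protects the primary estimand at almost no cost.

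**What to change.** In SAP 3.2, delete the conditional log step for office SBP. State that the primary estimate is the between-arm difference in change from baseline to 3 months, in mm Hg, from the GEE model with an identity link and robust (sandwich) standard errors, whatever the shape of the residuals. Residual plots then serve as diagnostics only, and any log-scale model becomes a sensitivity analysis.

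Treat office DBP the same way in SAP 4.2, and exempt office SBP and DBP from the general transformation sentence in Protocol section 13. The other secondary endpoints can stay as written.

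The cost is a few sentences across the two documents, with no change to sample size, data collection or participant burden. The edit should be dated before outcome data are analysed.

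### The primary GEE adjusts for neither baseline SBP nor the SBP stratum, names two different terms as the test, and plans a sensitivity model that may check nothing

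*SAP*

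**What the plan says.** SAP 3.2 and Protocol 13 specify a GEE with a treatment-by-visit interaction. Baseline, 3 months and 6 months are all levels of visit, so baseline SBP is a response row. No covariate is named for the primary model. Adjustment appears only as "Models will be adjusted for ZIP code or baseline blood pressure in sensitivity analyses" (SAP) and "Models will be adjusted for ZIP code or baseline BP in sensitivity analyses" (Protocol), with no statement of how the covariate enters.

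Randomisation is stratified at 140 mm Hg. SAP 3.1 gives the reason: "Blood pressure will be used as a stratification variable to ensure that people with varying degrees of hypertension are evenly distributed between interventions". The stratum returns only as a subgroup in SAP 3.4.

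On the test, SAP 3.2 first fits the visit term "with a product (interaction) term to compare changes across intervention". It then says the comparison of arms will be "performed by comparing the regression coefficient for treatment with zero", and this sentence carries the two-sided 0.05 rule at 3 months. The hypothesis reads: "The null hypothesis is that there will be no difference in office SBP between the two intervention arms". SAP 3.3 says: "The primary outcome is change in SBP between the two randomized assignments". Its power calculation is for 75 per arm and -5.8 mm Hg, "assuming a standard deviation of 11.85 and 11.4 for control and intervention groups based on the DASH-Sodium trial", without saying whether these are SDs of SBP or of change.

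**The concern.** There are three linked problems.

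1. **Precision.** The difference in change is valid, but in large samples it is never more precise than a contrast adjusted for baseline. Baseline SBP is the mean over three pre-randomisation visits that also decides entry (Protocol 5 and 7), so it is known for everyone randomised.
2. **Definition of the test.** In a treatment-by-visit model, the treatment coefficient is the arm difference at the reference visit. It is never the difference in change. The null hypothesis reads as a comparison of levels, while SAP 3.3 speaks of change. The only test that carries alpha should not be left to inference.
3. **An empty sensitivity analysis.** If baseline BP or ZIP code is added as a main effect while baseline stays a response row, it cancels from the change contrast. Agreement with the primary result would then look like robustness without being evidence of it.

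SAP 3.4 repeats the primary analysis in seven subpopulations and SAP 4.2 uses the same interaction form for the secondary outcomes, so the problems carry over.

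**Working it through.** **The plan's own figure.** The pooled SD is sqrt((11.85² + 11.4²)/2) = 11.63. The SE is sqrt((11.85² + 11.4²)/75) = 1.899, and 5.8/1.899 = 3.05. Two-sample power is 0.86 (noncentral t), against 0.85 stated, so the figure reproduces. It contains no baseline term.

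**Precision, with the SAP SDs read as SDs of 3-month SBP.** Let s0 be the baseline SD, s1 the 3-month SD and r their correlation. The documents give neither s0 nor r, so both are assumed.

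- Variance of change: s0² + s1² − 2·r·s0·s1
- Baseline-adjusted variance: s1²(1 − r²)
- Difference: (s0 − r·s1)², which is zero only when the slope r·s1/s0 equals 1

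Example with s0 = 8 and r = 0.3:

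- Change variances are 64 + 140.42 − 56.88 = 147.54 (control) and 64 + 129.96 − 54.72 = 139.24 (intervention). SE = sqrt(286.78/75) = 1.955 and power is 0.84.
- Adjusted: SE = sqrt(0.91 × 270.38/75) = 1.811 and power is 0.89.

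The formula columns use s0 = 8. The simulation used the planned stratified blocks and the 120 to <150 entry range (baseline SD 7.7, 27% at 140 or above), n = 150, an assumed 3/6-month residual correlation of 0.5, and 6,000 trials per cell. Its adjusted analysis is the GEE proposed below, with a small-sample-corrected robust SE.

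| r | Formula: planned | Formula: adjusted | Simulated: planned | Simulated: adjusted | Type I error: planned | Type I error: adjusted |
|---|---|---|---|---|---|---|
| 0.2 | 0.79 | 0.87 | 0.82 | 0.87 | 0.032 | 0.047 |
| 0.3 | 0.84 | 0.89 | 0.84 | 0.88 | 0.037 | 0.049 |
| 0.4 | 0.89 | 0.91 | 0.89 | 0.91 | 0.048 | 0.051 |
| 0.5 | 0.93 | 0.94 | 0.94 | 0.94 | 0.048 | 0.048 |
| 0.6 | 0.97 | 0.97 | 0.96 | 0.96 | 0.044 | 0.043 |

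Other baseline SDs, planned versus adjusted by formula:

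- SD 5: 0.85 versus 0.87 at r = 0.2, and within 1 point for r = 0.3 to 0.6
- SD 6: 0.84 versus 0.87 at r = 0.2, and 0.94 for both at 0.5
- SD 8.66 (uniform over 120-150): 0.77 versus 0.87 at r = 0.2, and 0.92 versus 0.94 at 0.5

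**Precision, with the SAP SDs read as SDs of change.** The planned test has power 0.86. Solving s0² + s1² − 2·r·s0·s1 = SD² for s1 with s0 = 8, the adjusted test has 0.94, 0.91, 0.88, 0.86 and 0.86 at r = 0.2 to 0.6.

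**Which term is tested (simulated, true effect -5.8).**

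- Treatment coefficient with baseline as reference visit: this equals the baseline arm difference and is significant in under 0.5% of trials.
- Treatment coefficient with 3 months as reference visit: this equals the unadjusted 3-month difference in levels, with power 0.86 to 0.89.
- Treatment by 3-month interaction: power 0.82 to 0.96 over the same r.

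The last two disagree on significance in 7-9% of trials, and in 14-17% if the true effect is -4 (r = 0.3 and 0.5).

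**The sensitivity model.** A covariate with one coefficient at all visits shifts every visit mean in an arm equally and drops out of the change contrast. In one simulated complete data set the interaction was -5.978970 (SE 1.642134) with no covariate, with baseline SBP, with the stratum and with ZIP code, under both independence and exchangeable working correlations. Over 12 complete data sets the largest change in the estimate or SE was 5e-14. With 15% dropout and baseline rows kept, the match is no longer exact: under independence, -4.103 unadjusted, -3.905 with baseline and -4.244 with ZIP code.

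**ZIP code in a model of follow-up rows only.** With 13 areas assumed (the number of communities in Protocol 5) and an uncorrected robust SE, type I error was about 0.07.

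**The case against.** The planned test is valid, with simulated type I error of 0.032 to 0.048. Baseline SBP is not ignored: it is balanced by stratification, used as a visit level, and named for a sensitivity model. The gain from adjustment needs both a low correlation and a wide baseline spread, and neither is documented. The SAP SDs are said to rest on 12-week means and variances, which favours the level reading over the change reading with its larger gain. All of this stands, and it limits the precision point to an improvement in efficiency.

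On the tested term, SAP 3.2 opens by describing a net effect from baseline to 3 months, Protocol 13 mentions only the product term, and alpha is tied to 3 months. The interaction is therefore the natural reading, and a test of the baseline arm difference is not credible. Nor does disagreement between two valid tests prove error inflation: the adjusted and planned tests themselves disagree in 4.7% of simulated trials at r = 0.3 and 1.6% at 0.5. That is also right. Yet the sentence that carries alpha names another coefficient, and no other section corrects it.

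On the sensitivity model, exact equality needs complete data, a main effect only, and baseline kept as a response row. The SAP plans for 15% attrition, so near-equality is the likelier outcome. The form of the model is still unspecified.

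**Conclusion.** The concern holds on all three parts, as a matter of efficiency and clarity rather than bias. Adjustment would raise power by about 8 points at r = 0.2 and 1 point at r = 0.5 if the baseline SD is 8. The gain at r = 0.2 is about 2 to 3 points for an SD of 5 to 6 and 10 points for 8.66, and it vanishes where the slope of 3-month on baseline SBP is 1. These figures rest on assumed correlations and baseline SDs, so the existence of a gain is firm but its size is not. No shortfall against 85% is shown, and on the change-SD reading the planned test meets it. The wording of the test is the weightier part, because two plausible readings have different power and can differ on significance. The adjusted sensitivity model adds nothing with complete data, and probably little with 15% dropout, unless its form is changed.

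**What to change.** - Make the primary model a GEE of the 3- and 6-month SBP with treatment by visit, baseline SBP by visit, and the SBP stratum. State a working correlation other than independence, and a robust variance with small-sample correction.
- Name the 3-month treatment contrast from this model as the single primary test, in place of the treatment coefficient, and word the null hypothesis to match.
- Keep the unadjusted difference in change (treatment by 3-month interaction) as the sensitivity analysis.
- Fit any ZIP-code adjustment as a main effect in the follow-up-rows model, with the small-sample correction.
- Use the same baseline adjustment for the continuous secondary outcomes.
- State in SAP 3.3 whether the two SDs are for SBP or for change.

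The cost is SAP wording and a few lines of code, since every covariate is already collected. It should be settled before assignments are unmasked.
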